16.1. PRIMARY EFFICACY

Unless otherwise indicated, all efficacy summaries and analyses will be presented based on the FAS.

16.1.1. TIME TO CONFIRMED CLINICAL RECOVERY THROUGH DAY 29, WITHOUT RE-HOSPITALIZATION THROUGH DAY 29

The primary efficacy endpoint is the time to confirmed clinical recovery through Day 29, i.e., fit for discharge (defined by achieving a score of 6, 7, or 8 on the 8-point ordinal scale for clinical severity), without being re-hospitalized through Day 29.

It is to be noted that:

- The re-hospitalization-free requirement does not apply to patients who achieved an ordinal scale score of 6 that were never discharged from the hospital before Day 29. For such patients, the re-hospitalization-free requirement is superseded by not having a subsequent worsening on the ordinal scale score (i.e., a score < 6 on the ordinal scale for clinical severity) that would remain until Day 29;
- Patients achieving a score of 7 on the ordinal scale for clinical severity discharged to hospice care will be considered as not fit for discharge in the analysis.

The ordinal scale for clinical severity is as follows:

1. Death;
2. Hospitalized, on invasive mechanical ventilation or ECMO;
3. Hospitalized, on non-invasive ventilation or high-flow oxygen devices;

CCI [Redacted]

Master Statistical Analysis Plan

4. Hospitalized, requiring supplemental oxygen;
5. Hospitalized, not requiring supplemental oxygen, requiring ongoing medical care (COVID-19 related or otherwise);
6. Hospitalized, not requiring supplemental oxygen, no longer requires ongoing medical care;
7. Not hospitalized, limitation on activities and/or requiring home oxygen;
8. Not hospitalized, no limitations on activities.

Time to confirmed clinical recovery through Day 29, without re-hospitalization through Day 29, will be measured in days from the date of Study Day 1 (refer to Section 6.1):

- Time to confirmed clinical recovery through Day 29, without re-hospitalization through Day 29 (days) = (Date of event – Date of Study Day) + 1

Refer to Section 6.1 for the definition of Study Day 1.

The following algorithm will be followed to determine if a patient met the event (i.e., confirmed clinical recovery through Day 29, without rehospitalization through Day 29) or should be censored:

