1. First, the patient’s alive status by Day 29 will be verified as per data collected on the *Death Details* page of the eCRF. If the patient died before or on Day 29, he/she will be censored at Day 29. If the patient has not died by Day 29, then go to step 2;
2. Second, the patient’s study discontinuation status by Day 29 will be verified as per data collected on the *Disposition* page of the eCRF. If the patient discontinued from the study before or on Day 29, he/she will be censored at date of discontinuation from study. If the patient was still ongoing in the study at Day 29, then go to step 3;
3. Last, it will be verified if a patient had a score of 6, 7 or 8 on the 8-point ordinal scale (as captured on the *Ordinal Scale for Clinical Severity* page of the eCRF) before or on Day 29:
 - a. For patients who had a score of 6 on the 8-point ordinal scale and were never discharged from the hospital before Day 29, it will be checked if patient worsened on the 8-point ordinal scale (i.e., had a score < 6) before or on Day 29:
 - i. If so (i.e., patient worsened) and patient never subsequently re-reached a score of 6 before or on Day 29, the patient will be censored at Day 29;
 - ii. If so (i.e., patient worsened) but patient subsequently re-reached a score of 6 before or on

- Day 29, the patient will be considered as having the event and the date of the event will be the earliest date on which the patient re-reached a score of 6;
- iii. If not (i.e., patient did not worsen), the patient will be considered as having the event and the date of the event will be the earliest date on which the patient had a score of 6 before or on Day 29;
- b. For patients who had a score of 7 on the 8-point ordinal scale, it will first be verified if patient was discharged to hospice care as per data captured on the *Hospitalization* page of the eCRF.
 - i. If so (i.e., patient was discharged to hospice care), the patient will be considered as not fit for discharge and will be censored at Day 29;
 - ii. If not (i.e., patient was discharged, but not to hospice care), then go to step c.

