 - c. For patients who had a score of 7 (discharged, but not to hospice care) or 8 on the 8-point ordinal scale, it will be verified if patient was re-hospitalized before or on Day 29 as per data captured on the *Hospitalization* page of the eCRF. To do so, it will be checked if a patient had at least one record where the hospitalization start date is after the earliest date on which the patient had a score of 7 or 8 but before or on Day 29.
 - i. If so (i.e., patient was re-hospitalized), the patient will be censored at Day 29;
 - ii. If not (i.e., patient was not re-hospitalized), the patient will be considered as having the event and the date of the event will be the earliest date on which patient had a score ≥ 6 before or on Day 29;
 - d. Patients who never had a score of 6, 7 or 8 on the 8-point ordinal scale, did not discontinue from the study or died before or on Day 29 will be censored at Day 29

Refer to [Figure 2](#) for a schematic of the primary endpoint determination of date of event and censoring.

[figure not shown]
CCI

PPD

[figure not shown]
Version Number: Amendment 1, v1.0
Version Date: 23Apr2021

CCI

Figure 2 Schematic of Determination of Primary Efficacy Endpoint Date of Event or Censoring

* For patients who had a score of 6, worsened, *re*-reached a score of 6, and were never discharged from the hospital before or on Day 29, earliest date on which the patient *re*-reached a score of 6.

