16.1.2. MISSING DATA IMPUTATION METHOD FOR PRIMARY EFFICACY ENDPOINT

For the time to confirmed clinical recovery (days) through Day 29, without re-hospitalization through Day 29, missing ordinal scale for clinical severity scores and missing hospitalization data will not be imputed before applying the censoring rules for the main analysis of the primary efficacy endpoint (refer to Section 16.1.1).

[figure not shown]

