16.1.5. SUPPLEMENTARY ANALYSES FOR PRIMARY EFFICACY ENDPOINT

The following supplementary analyses to the main analysis of the primary efficacy endpoint will be performed:

- The main analysis to the primary efficacy endpoint will be repeated (refer to Section 16.1.3) but without country (region; refer to Section 7.5) included as stratification variable;
- The main analysis of the primary efficacy endpoint will be repeated but without the requirement for follow-up confirmation. That is, for this analysis, patients will be considered as having met the event as soon as they reach a score of 6, 7 or 8 on the 8-point ordinal scale, regardless of if they subsequently worsened or were re-hospitalized before or on Day 29, exception of patients with a score of 7 discharged to hospice care who will

still be considered as not having the event;

- The main analysis of the primary efficacy endpoint will be repeated for each subgroup defined in Section 7.7. For subgroups corresponding to one of the factors included in the main model, the corresponding factor will be excluded from the model. For example, the remdesivir use at baseline (yes/no) stratification variable as captured on the IWRS will not be included in the model for the analysis of the patients who received remdesivir at randomization as captured on the IWRS subgroup, and analysis of the patients who did not receive remdesivir at randomization as captured on the IWRS subgroup.

[figure not shown]

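### SAP 16.1.1 leaves the primary event status open after a second in-hospital worsening, and dates the same relapse differently according to later discharge

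*SAP*

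**What the plan says.** Master SAP 16.1.1 defines the primary event and its date. The sub-protocol SAPs refer back to it for the definition.

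- **Note at the start of the section.** For a patient who scores 6 and is never discharged before Day 29, the re-hospitalization condition is replaced by a worsening condition. What disqualifies is a later score below 6 "on the ordinal scale for clinical severity) that would remain until Day 29".
- **Step 3a.i** (never discharged). If the patient worsened "and patient never subsequently re-reached a score of 6 before or on Day 29, the patient will be censored at Day 29".
- **Step 3a.ii** (never discharged). If the patient worsened but got back to 6, the patient has the event, and its date "will be the earliest date on which the patient re-reached a score of 6".
- **Step 3c.i** (non-hospice 7, or 8). The only check is for an admission after the first 7 or 8. "If so (i.e., patient was re-hospitalized), the patient will be censored at Day 29".
- **Step 3c.ii** (same patients, not re-hospitalized). "the date of the event will be the earliest date on which patient had a score ≥ 6 before or on Day 29".
- **Figure 2 footnote.** The re-reached date is limited to patients who worsened, recovered "and were never discharged from the hospital before or on Day 29, earliest date on which the patient" got back to 6.

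Protocol 8.1.1 treats a patient as fit for discharge after a single score of 6, 7 or 8 during the study. The primary endpoint adds only that the patient is not re-hospitalized through Day 29.

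**The concern.** There are two separate problems.

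**Event status.** Step 3a.ii looks no further once 6 has been re-reached. A never-discharged patient who then worsens a second time and is still below 6 on Day 29 has an event under 3a.ii, but not under the note. Two programmers could follow the section in good faith and disagree on whether this patient recovered.

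**Event date.** Step 3c looks for re-admission but not for a fall below 6 before discharge. The same in-hospital course therefore gets one date if the patient stays in hospital and an earlier one if the patient is later discharged. For the discharged patient, a recovery called confirmed can precede a long spell on respiratory support.

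These steps feed the stratified log-rank test, the Cox hazard ratio and the futility looks. Among the sub-protocols shown, those analyses remain planned only for COV-01-004. COV-01-001 and COV-01-005 have dropped inference but still report event counts and Kaplan-Meier estimates from the same variable.

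**Working it through.** **Step 1: apply the rules to score histories.** The last column applies two changes. For never-discharged patients, the last worsening governs. For discharged patients, the date is the first score of 6 or more after the last in-hospital score below 6.

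| History | Steps as written | Note in 16.1.1 | Changed rule |
|---|---|---|---|
| 1. 6 on Days 5–6, 4 on Days 7–29, never discharged | Censored Day 29 (3a.i) | No event | Censored Day 29 |
| 2. 6 on Days 5–6, 3 on Days 7–19, 6 on Days 20–29, never discharged | Event Day 20 (3a.ii) | Event | Event Day 20 |
| 3. 6 on Days 5–6, 4 on Days 7–19, 6 on Days 20–21, 4 on Days 22–29, never discharged | Event Day 20 (3a.ii, literal), or censored Day 29 (3a.i applied to the last worsening) | No event | Censored Day 29 |
| 4. As 3, but 4 on Days 22–25 and 6 on Days 26–29 | Event Day 20 (3a.ii) | Event | Event Day 26 |
| 5. As 2, but discharged on Day 21, no readmission | Event Day 5 (3c.ii) | Not applicable | Event Day 20 |
| 6. Discharged Day 10, readmitted Days 12–13, discharged Day 14 | Censored Day 29 (3c.i) | Not applicable | Censored Day 29 |
| 7. 6 on Day 8, no relapse, discharged Day 10 | Event Day 8 (3c.ii) | Not applicable | Event Day 8 |

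History 3 is the conflict over status. Histories 2 and 5 are the conflict over dates: the relapse is the same, but the dates differ by 20 − 5 = 15 days. In history 5 the Day 5 recovery is followed by 19 − 7 + 1 = 13 days at score 3. Only courses with an in-hospital relapse change.

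**Step 2: does a planned analysis isolate this?** The supplementary analysis in SAP 16.1.5 counts the first 6, 7 or 8 "regardless of if they subsequently worsened or were re-hospitalized before or on Day 29". It also gives history 5 Day 5, so comparing it with the main analysis shows nothing for that patient. It makes history 6 an event, which is a different change. The sensitivity analyses in 16.1.4 vary the stratification data and the handling of study discontinuation, not this date. Recovery status at Days 8, 15 and 29 and the shift tables would reveal a relapse, but they do not re-estimate time to recovery.

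**Step 3: the plan's power figure.** Inputs from SAP 7.1 and 16.5.1: 490 events, hazard ratio 1.364, one-sided 0.025, futility looks at 123 and 270 events with p-value boundaries 0.503 and 0.175.

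- Single look: Φ(√(490/4) × ln 1.364 − 1.96) = Φ(11.07 × 0.3104 − 1.96) = Φ(1.476) = 93.0%.
- With both futility looks, from a joint normal calculation: 88.3%, and null stopping probabilities of 0.497 and 0.346. All three match the SAP.

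**Step 4: size of the dating effect.** The documents give no in-hospital relapse rate, so the rates here are assumptions. The model was a single-look, unstratified log-rank test with 350 patients per arm and 20,000 runs per scenario. The control hazard was ln 2/15 per day to Day 15, then 0.0243; the active hazard was 1.364 times that. Simulated events averaged 490.0.

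| Share of recoveries dated 2–15 days early, both arms | Power | One-sided error |
|---|---|---|
| 0% | 93.0% | 2.5% (nominal) |
| 5% | 93.0% | not given |
| 10% | 92.6% | 2.7% |

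The simulation standard error is √(0.93 × 0.07/20,000) = 0.2 points for power and √(0.025 × 0.975/20,000) = 0.1 points for error. The medians move 0.3 days earlier at 5% and 0.5 to 0.6 days earlier at 10%.

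The effect of history 3 on status was not simulated. Each such patient changes one event, or 1/490 = 0.2% of the planned number.

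**The case against.** **Step 3c.ii follows the protocol.** One qualifying score is enough for fit-for-discharge, and re-hospitalization is the only confirmation added. The SAP note openly gives never-discharged patients a separate rule, because re-admission cannot apply to them. This stands. A reader might infer that 3c.ii is simply wrong, but the documents do not say that recovery means the final one. What remains is that 3a.ii already departs from first-score dating for one group, without a stated reason.

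**Step 3a.i, applied to the last worsening, already censors history 3, and the note shows the intent.** That is a fair reading, but the steps do not say which worsening is meant. The Figure 2 schematic could not be read in the text available, only its footnote. The conflict also needs two in-hospital worsenings, so it may be rare.

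**A reader might infer that early dating inflates the type I error.** Such a result can be produced by assuming unequal rates, for example 10% of recoveries dated early in one arm and 5% in the other. The rejection rate is then 2.9% to 3.4% when the active arm has more, but 1.8% when control has more. No document supports those rates or a difference between arms. Under the protocol's single-score definition, such a difference would be a real difference in the endpoint.

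**Aligning the dates has a cost.** Score 5 covers any active medical issue that needs in-hospital care, so a one-day dip to 5 for an unrelated reason would reset the event date. This stands, and it is why keeping 3c.ii is an acceptable option.

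**Conclusion.** The event-status point holds as a defect of wording. Step 3a.ii read literally contradicts the note in its own section, and the alternative reading through 3a.i leaves the primary event with two possible values for the same patient. It should be settled before the COV-01-004 primary analysis.

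The dating point holds as an inconsistency. The two rules are explicit, and no planned analysis isolates the effect of choosing one over the other. First-score dating for discharged patients is nevertheless compatible with the protocol.

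The likely size is small. With equal rates of up to 10% the effect on power and type I error is negligible. That rests on assumed rates and on a simplified single-look model without the futility looks. No direction of bias can be shown from the documents.

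**What to change.** **Step 3a and the Figure 2 footnote.** State that the last worsening governs. A never-discharged patient below 6 at Day 29 is censored at Day 29; otherwise the event date is the start of the final run at 6. While editing, align the cut-off: step 3a refers to discharge before Day 29 and the footnote to discharge before or on Day 29, so a Day 29 discharge now fits both 3a and 3c.

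**Step 3c.ii.** Choose one:

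- Date the event at the first score of 6 or more after the last recorded in-hospital score below 6 before discharge, and list this in SAP 3.3, which now records one unrelated change.
- Keep first-score dating, give the reason for treating the two groups differently, and add one sensitivity analysis using the date above with the re-hospitalization rule in 3c.i unchanged. The analysis in 16.1.5 cannot serve, because it also drops the re-hospitalization requirement.

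**Cost.** A sentence in each sub-step, the footnote, one derived date, and either a line in SAP 3.3 or one extra analysis. Only recorded in-hospital scores are used, so the rule in 16.1.2 that "missing ordinal scale for clinical severity scores and missing hospitalization data will not be imputed" is unaffected, and no daily scores after discharge are needed. The downside is that discharged patients gain an in-hospital worsening check that the protocol does not spell out, in the main analysis under the first option and only in the sensitivity analysis under the second.

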### 1.3 Example Schedule of Activities

	Screening	Baseline				
Day (± Window)	Day -1 or Day 1	Day 1	Daily Until Hospital Discharge (or Daily Until Day 29 While in Hospital)	Day 15 a (±2 days)	Day 29 a (±3 days)	Day 60 a (±4 days) (End of Study)
ELIGIBILITY						
Informed consent	X					
Demographics	X					
Relevant medical history b	X					
Review of SARS-CoV-2 diagnostic tests (obtained during the previous 72 hours, if available)	X					
SARS-CoV-2 diagnostic test c	X					
Inclusion and exclusion criteria	X	X				
12-lead electrocardiogram	X					
STUDY INTERVENTION						
Randomization		X				
Administration of study treatment		Defined in sub-protocol				
Treatment with SoC		SoC will be based on the practices of the study center				
STUDY PROCEDURES						
Physical examination (including height and weight) d	X					
Vital signs, including body temperature, pulse rate, blood pressure, respiratory rate, SpO 2 , FiO 2 e		X f	X	X g	X g	
CCI						
Ordinal scale		X f	X	X	X	X

	Screening	Baseline				
Day (± Window)	Day -1 or Day 1	Day 1	Daily Until Hospital Discharge (or Daily Until Day 29 While in Hospital)	Day 15 a (±2 days)	Day 29 a (±3 days)	Day 60 a (±4 days) (End of Study)
Clinical assessments b		X f	X	X	X	X i
Assessment of floor status (ICU yes/no)		X	X g	X g	X g	
Assessment of rehospitalization for discharged patients j				X	X	X
Concomitant medication review (including use of vasopressors)	X	X f	X	X	X	X
Adverse event evaluation	X	X	X	X	X	X
SAFETY LABORATORY						
Clinical safety laboratory assessments	X k,l	X f,m,n	Days 3 o , 8 m , 22 m , and at discharge m,p All other days while in hospital q	X m,r	X m	
Pregnancy test for females of childbearing potential	X k					
RESEARCH LABORATORY						
CCI						

Abbreviations: ARDS=acute respiratory distress syndrome; eCRF=electronic case report form; FiO2=fraction of inspired oxygen; ICF=informed consent form; ICU=intensive care unit; **CCI**; SARS-CoV-2= severe acute respiratory syndrome coronavirus 2; SoC=standard of care; SpO2=oxygen saturation.

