Note: Additional assessments, if required, will be defined in the sub-protocol.

a These visits will be performed even if a patient has already been discharged. If discharged prior to scheduled visit, these visits will be conducted via telemedicine. For visits conducted by telephone, it may not be possible to perform some scheduled assessments (eg, vital signs). The Day 29 assessments will also be performed, where possible, for patients who discontinue the study prematurely.

b Medical history includes estimated date and time of first COVID-19 related symptoms and co-morbidities (eg, respiratory [including date of diagnosis of ARDS, if present], cardiovascular, metabolic, malignancy, endocrine, gastrointestinal, immunologic, renal).

- c Oropharyngeal/nasal swab for polymerase chain reaction determination of SARS-CoV-2 or for SARS-CoV-2 antigen testing. Only to be performed if no diagnostic test results are available that have been obtained during the previous 72 hours.
- d If height and/or weight cannot be obtained at the Screening Visit (Day -1 or Day 1), these parameters can be recorded as a combination of patient-reported data and data obtained from recent medical records (ie, at hospital admission).
- e For patients requiring high-flow oxygen, mechanical ventilation (invasive/noninvasive), or extracorporeal membrane oxygenation only, provide FiO2 requirement.
- f Baseline assessments should be performed prior to study drug administration.
- g To be assessed only while hospitalized.
- h Includes oxygen requirement (ie, mode of delivery/liters of oxygen flow, FiO2 requirement), stop date of oxygen for patients who were discharged on home oxygen, extracorporeal membrane oxygenation support, noninvasive or invasive ventilator requirement, including start and stop of low- or high-flow oxygen supply or of any form of ventilation, and need for renal replacement therapy. Noninvasive ventilation refers to the delivery of mechanical ventilation to the lungs using techniques that do not require an endotracheal airway.
- i Only stop date of oxygen for patients who were discharged on home oxygen.
- j Information recorded is yes/no, hospitalization date, discharge date.
- k Laboratory tests performed within the 48 hours prior to enrollment will be accepted for determination of eligibility.

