Patients will be screened on Day -1 (the day before the first dose of study treatment [candidate agent or placebo/SoC] is scheduled) or Day 1 and will remain in the hospital from Day 1 until discharge. All patients will receive SoC treatment, either with blinded candidate agent or matching blinded placebo. The SoC will be based on appropriate local written guidelines in place at a site at the time of treatment in the study; the SoC may change during the course of the study as new information becomes available about treating COVID-19. Dosing with the study treatment (as an add-on to SoC) will commence on Day 1. Patients will be assessed daily while hospitalized. If they are discharged from the hospital prior to Day 15, they will have study visits at Days 15 and 29 as an outpatient by telemedicine. The last day of primary assessments will be Day 29. An end-of-study visit will be conducted on Day 60 ( $\pm 4$  days) via telemedicine (unless the patient is still hospitalized in which case it would be conducted in person).

Sub-protocols will outline the scientific rationale, additional eligibility criteria (if necessary), treatment dose and regimen, statistical analysis populations, and other specifics unique to each candidate agent. The sub-protocols may define AEs of special interest and can include pharmacokinetic (PK) and/or pharmacodynamic assessments that are appropriate for the specific candidate agent. The endpoints specified in this Master Protocol will not be altered in the sub-protocols, but the sub-protocol may define additional endpoints. In order to enroll, a patient must meet all entry criteria for both the Master Protocol and at least one active sub-protocol.

The study will evaluate the candidate agents as an add-on to the SoC to assess safety and efficacy. Interim analyses may be performed for each candidate agent to evaluate futility for candidate agents.

Patients will be stratified at randomization by baseline clinical severity of 2 on the 8-point ordinal scale (yes/no) and remdesivir use at baseline (yes/no).

Enrollment of patients will be continuous throughout the study for each candidate agent until the total number of planned patients for that agent is enrolled or until futility criteria is met at the interim analyses, or if the agent is considered unsafe.

In addition, centers may elect to participate in separate Investigator-initiated studies collecting additional data on patients (eg, PK analyses), as their resources permit.

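### Master SAP 16.1.1 dates recovery and starts the readmission check from recorded ordinal scores only, so a patient with no 7 or 8 entered by the discharge day can be misdated, lost, left unclassified or wrongly counted as recovered

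*SAP*

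**What the plan says.** Master SAP 16.1.1 sets event status and date in three steps. After checking death and study discontinuation, step 3 turns to the Ordinal Scale page, where "it will be verified if a patient had a score of 6, 7 or 8 on the 8-point ordinal scale" by Day 29.

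- **3a** covers the inpatient route: "For patients who had a score of 6 on the 8-point ordinal scale and were never discharged from the hospital before Day 29".
- **3b** censors patients scored 7 who were discharged to hospice.
- **3c** takes patients with a 7 or 8 and looks for an admission "where the hospitalization start date is after the earliest date on which the patient had a score of 7 or 8" and no later than Day 29. If there is none, the "date of the event will be the earliest date on which patient had a score" of at least 6.
- **3d** censors at Day 29 anyone who never had a 6, 7 or 8.

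The Hospitalization page serves only the hospice and readmission checks. Section 16.1.2 imputes neither missing scores nor missing hospitalization data.

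Master Protocol 1.3 schedules the scale under the column "Daily Until Hospital Discharge (or Daily Until Day 29 While in Hospital", and then at Day 15 (±2), Day 29 (±3) and Day 60. Section 4.1 agrees: "Patients will be assessed daily while hospitalized", and for those discharged before Day 15, "they will have study visits at Days 15 and 29 as an outpatient by telemedicine". On rehospitalization, the schedule footnote states: "Information recorded is yes/no, hospitalization date, discharge date".

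**The concern.** Scores 7 and 8 mean that the patient is out of hospital, yet the schedule moves to widely spaced calls once that happens. No passage says that the discharge-day entry must be the post-discharge category. A patient going home on oxygen cannot pass through 6, because 6 excludes supplemental oxygen. That patient's first qualifying score may therefore come from the next call.

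Two things are at stake. The recorded time can reflect the call calendar and not the illness. And the endpoint's own condition, no rehospitalization through Day 29, can go unchecked between the real discharge and the first recorded 7 or 8.

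**Working it through.** **1. Tracing the rule.** Each case follows the schedule. Study days are counted as in Master SAP 6.1.

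| Case | Course | Result under 3a–3d |
|---|---|---|
| (i) | Score 6 Day 4, home Day 5, readmitted Day 8, home Day 12, first 7 on Day 15 | The Day 8 admission is not after Day 15, so 3c finds no readmission: confirmed recovery dated Day 4 |
| (ii) | Last score 4, home on oxygen Day 6, next score at the Day 15 visit | Event dated Day 13 to 17, which is 7 to 11 days late |
| (iii) | Last score 4, home Day 20, Day 29 visit held on Day 31 | No score of 6 or more by Day 29, so 3d censors a patient who had been home for 9 days (29 − 20) |
| (iv) | Score 6, home Day 20, first 7 on Day 31 | Not 3a (was discharged), not 3b or 3c (no 7 or 8 by Day 29), not 3d (had a 6) |

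Cases (i) and (iv) need no 7 or 8 entered by the discharge day. Cases (ii) and (iii) need no score of 6 or more by then. Three of the seven permitted days for the Day 29 visit (30, 31, 32) fall after Day 29.

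**2. Whether another rule repairs this.** The discharge-data mapping in Master SAP 6.3 and 6.4 is for by-visit summaries. The analyses in 16.1.4 and 16.1.5 rest on the same score records. For the second key secondary endpoint, 16.2.2.1 carries a last 7 or 8 forward to Day 29; the primary endpoint has no comparable rule.

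**3. The plan's own figure.** With 490 events, HR 1.364 and one-sided 0.025, power without futility looks is Φ(ln 1.364 × √490 / 2 − 1.96) = Φ(3.436 − 1.960) = 93.0%. Applying the futility bounds at 123 and 270 events (p = 0.503 and 0.175) gives 88.3%, as stated. That figure is not in dispute.

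**4. Size.** The documents give no affected share, so it is assumed and varied. The simulation used exponential recovery times with medians of 11 and 15 days, in whole days, with visits uniform on Days 13–17 and 26–32. Affected recoveries took the date of the next visit.

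| Affected share, agent / placebo | HR | Recoveries lost per 350 + 350 |
|---|---|---|
| 0 / 0 | 1.37 | 0 |
| 10% / 10% | 1.35 | about 8 |
| 20% / 20% | 1.35 | about 16 |
| 30% / 30% | 1.34 | about 23 |
| 20% / 10% | about 1.27 | – |
| 10% / 20% | about 1.42 | – |

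The mean delay per affected recovery is about 8 days. At 10% in each arm the medians move from 11 and 15 to 13 and 16, so the gap goes from about 4 to 3 days.

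This model expects 350 × (0.839 + 0.738) = 552 recoveries, against the plan's 490. A second model sets a never-recovering share of 1 − 490/552 = 11.2% in both arms. It gives 490 events and 84% power at the final test with nobody affected, 483 and 82% at 10%, and 456 and 80% at 50%. The 84% is not comparable with 88.3%: this model's HR is about 1.31 and it has no futility looks. Only the change across shares is informative.

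**The case against.** The strongest reply is that sites may simply enter a 7 or 8 on the discharge day. The schedule already places laboratory tests at discharge, and the SAP speaks of discharge data. Form-completion guidelines, which are not among the documents, may settle it. If so, most of these cases vanish. This stands as a condition on the point, since the documents neither require nor exclude such an entry.

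Second, Protocol Tables 2 and 3 imply that a patient off oxygen and ready to leave is a 6, not a 5. That narrows cases (ii) and (iii) mainly to home oxygen, whose frequency is not given. It does not help with (i) and (iv), which arise from a 6.

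Third, cases (iii) and (iv) as traced read Day 29 as a study day. Reading it as the visit with its window would rescue both. It would not touch (i) or (ii), and Master SAP 6.1 favours the study-day reading.

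Fourth, Figure 2 of the SAP, which charts this algorithm, is not legible in the copy reviewed. The missing branch in (iv) is therefore a statement about the text of 3a–3d only.

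Finally, COV-01-001 and COV-01-005 make no inference on this endpoint. They still report Kaplan-Meier summaries on this definition, and COV-01-004 keeps the full analysis.

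**Conclusion.** The point holds conditionally. As written, step 3 can misclassify protocol-compliant patients on the primary endpoint, and case (i) conflicts with the endpoint's own definition. This is a fault in a stated rule, not only a missing detail.

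Three stronger readings are tempting and not supported:

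- **A large loss of power or effect.** With equal shares the hazard ratio barely moves, and power falls by about 2 points at 10%.
- **A systematic penalty on effective agents.** That needs more home-oxygen discharges on the agent. An effective agent might instead send fewer patients home on oxygen, and the bias would then run the other way.
- **Everyone recovering after the Day 15 visit goes unscored until Day 29.** Inpatients are scored daily; the gap opens only at discharge.

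The sizes rest on assumed shares, exponential recovery times and uniform visit days.

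**What to change.** In Master SAP 16.1.1 step 3:

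- Treat the first live, non-hospice discharge date on the Hospitalization page as reaching a score of at least 7. Exclude transfers to another acute hospital where these can be identified. The event date is then the earlier of that date and the first score of 6 or more.
- Start the 3c readmission check from that discharge date.
- Apply 3c to every patient discharged by Day 29, including those whose only qualifying score is 6.

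Under these rules case (i) is censored for readmission, (ii) is dated Day 6, (iii) is an event on Day 20, and (iv) falls under 3c. Figure 2 should be aligned.

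The cost is SAP wording and programming. The SAP already reads admission dates from the Hospitalization page in 3c, and stop dates and outcomes in 16.2.1.1. The only outcomes named there are the hospice ones, so first confirm which discharge outcomes the page records. The change should be made before the primary-analysis lock for COV-01-004.
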